8 PHARMACOKINETIC VARIABLES AND ANALYSES

PK analyses will be performed using the PK set.

Descriptive statistics for the ACT-539313 plasma concentrations collected prior to the morning dosing at Week 4, Week 8 and Week 12 will be provided by age group and overall: n, mean, SD, CV%, m (number of non-zero concentrations), geometric mean, geometric SD, geometric CV%, median, minimum and maximum. These concentration values will also be displayed graphically by visit: scatter plots vs BMI by sex; and boxplots for age categories (18–29, 30–55 years) and all ages combined.

Concentration values below the lower limit of quantification will be displayed in listings as 'BLQ' and handled as zero in the calculations for mean, CV%, SD, median, minimum,

ACT-539313		Statistical Analysis Plan
ID-082A201	Confidential	for Clinical Study Report
1 April 2022, page 38/60	Confidential	Version 3
		Doc No D-22.100

and maximum, but handled as missing for the calculation of the geometric mean, geometric SD, and geometric CV%.

All individual ACT-539313 plasma concentration data will be listed.

Plasma samples might also be used by Idorsia Preclinical Pharmacokinetics and Metabolism department for exploratory assessments of circulating metabolites of ACT-539313.

9 GENERAL STATISTICAL METHODOLOGY

9.1 General rules for data presentations

Data are listed and summarized as described below.

The tables will use the following header structure (label and order):

ACT-539313 100 mg	Placebo
N = xxx	N = xxx

Where N indicates the total number randomized or treated appropriate to the analysis set in the corresponding treatment group, unless otherwise specified.

All listings will be sorted by randomized treatment or actual treatment received (appropriate to the analysis set), subject number (ascending) and, when appropriate, by visit / date of assessment (ascending). Listings related to the SCR set will present a treatment group label 'screening failure' to indicate study participants who were not randomized and will be listed after the study participants who were randomized or received study treatment, as relevant.

Unless noted otherwise, the following descriptive statistics will be used to summarize data: number (%) of study participants for categorical variables, or descriptive statistics (number of non-missing values, mean, SD, median, Q1, Q3, minimum, maximum) for continuous variables.

9.2 Handling of missing dates

An incomplete date (day or month missing), or missing concomitant therapy / AE date, will be imputed as described in Table 5. The 'lower limit' and 'upper limit' refer to the earliest and latest possible dates, respectively.

As an example: if concomitant therapy start date / AE onset date is MAR2021 (day missing), the lower limit is 01MAR2021 and the upper limit is 31MAR2021; if concomitant therapy start date / AE onset date is 2021 (day and month missing), the lower limit is 01JAN2021 and the upper limit is 31DEC2021.

Table 5	Imputation rules for an incomplete or missing concomitant therapy
	or AE date

Field	Incomplete date	Missing date
Concomitant therapy end date / AE resolution date	The upper limit.	No imputation. The therapy / AE is considered as ongoing.
Concomitant therapy start date / AE onset date	The rules below apply in the order presented: 1. If the (imputed) concomitant therapy / AE end date is on or after the start of study treatment, and if the study treatment start falls within the upper and lower limits (inclusive), the study treatment start date is used.	Whichever is the earlier of the concomitant therapy end date / AE resolution date or study treatment start date.
	2. If the concomitant therapy end date / AE resolution date is missing, and if the study treatment start falls within the upper and lower limits (inclusive), the study treatment start date is used.	
	3. In all the other cases, the lower limit is used.	

AE = adverse event.

The purpose of imputing concomitant therapy / AE dates is only to assign a concomitant therapy / AE to a specific study period for the summary tables. No imputed date is considered in the medical evaluation or causal relationship to an individual AE.

10 INTERIM ANALYSES

No interim analysis will be performed for determining whether to stop (or modify) the study early (i.e., no hypothesis testing will be conducted *ad interim*).

11 GENERAL DEFINITIONS AND DERIVATIONS

11.1 Treatment start and end dates

Study treatment start or end date is the earliest or latest, respectively, date of dose intake recorded on the 'Study Treatment Log' page.

11.2 Study periods

The Screening period is defined as the time from the informed consent date until one day before the study treatment start date, or date of screening failure.

The treatment period is defined as the time from the day of study treatment start until the day of EOT (Week 12), or, for those who prematurely discontinued study treatment (i.e., those without an EOT date), until the day of study treatment end date. In case of missing

ACT-539313		Statistical Analysis Plan
ID-082A201	Confidential	for Clinical Study Report
1 April 2022, page 40/60	Confidential	Version 3
		Doc No D-22.100

study treatment end date, EOT will be imputed using the last available visit/assessment date.

The safety follow-up period is defined as the time from one day after EOT until EOS date.

11.3 Treatment day and Study day

The Treatment day for an assessment or event will be calculated using the study treatment start date as reference.

For assessments/events occurring on or after the start date of study treatment, Treatment day will be positive and will be calculated as:

Treatment day (days) = Date of assessment/event - Start date of study treatment + 1 day

The first day of study treatment is Treatment day 1.

For all assessment/events occurring prior to the start date of study treatment, Treatment day will be negative and will be calculated as:

Treatment day (days) = Date of assessment/event – Start date of study treatment

The Study day for an assessment or event will be calculated using the randomization date as reference. For assessments/events occurring on or after the randomization date, Study day will be positive and will be calculated as:

Study day (days) = Date of assessment/event - randomization date + 1 day

The day of randomization date is Study day 1.

For all assessment/events occurring prior to the randomization date, Study day will be negative and will be calculated as:

Study day (days) = Date of assessment/event – randomization date

Treatment day and/or Study day will be displayed in the data listings as appropriate.

11.4 Baseline

Baseline is the last non-missing assessment performed or value measured before or on the day of first dose of study treatment, unless otherwise defined in the specific analysis section.

The baseline number of BE days per week is defined as the number of diary days with at least one BE episode divided by the total number of diary days during the 14 days prior to randomization (Study day -14 to -1), times 7 [see Section 6.1.1 for definition of diary day]. A minimum of 6 entries for each of the 2 weeks preceding randomization is required per inclusion criteria to ensure study participant compliance with filling in the BE diary.

ACT-539313		Statistical Analysis Plan
ID-082A201	Confidential	for Clinical Study Report
1 April 2022, page 41/60	Confidential	Version 3
		Doc No D-22 100

Study participants with no data for a given parameter before the first treatment administration will have a missing baseline (and missing change from baseline) for this parameter.

11.5 Change from baseline

The change from baseline is defined as the post-baseline value (any assessment performed after baseline and up to EOS) minus the baseline value. A positive number indicates an increase as compared to baseline.

11.6 Missing data patterns

A monotone missing data pattern is defined as follows: given a dataset with variables Y1, Y2, ..., Yt (in that order) and Vj is missing for a particular subject, then all subsequent variables Vk, k > j, are missing for that subject. In addition, given the same dataset and Vj is observed for a particular subject, then all previous variables Vk, k < j, are also observed for that subject. Monotone missing data patterns are typically encountered when a subject prematurely withdraws from a study and is expected to be more likely seen than non-monotone missing data patterns.

In the examples below, an 'X' indicates that the variable is observed in the corresponding group and a '.' means that the variable is missing.

Subject	Y1	Y2	¥3
1	Х	Х	Х
2	Х	Х	
3	Х		

Example of monotone missing data patterns:

When missing data are non-monotone, data can also be missing at intermediate visits (i.e., missing at a given visit, but observed again at the next visit). Non-monotone missing data patterns are commonly turned into monotone missing data patterns using MI (based on MCMC), which are then subsequently analyzed using MI methods based on monotone missing data.

Example of non-monotone missing data patterns:

Subject	Y1	Y2	Y3
1	X	Х	Х
2		Х	Х
3			Х
4		Х	
5	Х		Х

11.7 Time window definitions for calculating efficacy and safety endpoints collected through diary

BE episodes (efficacy) and daytime sleepiness (safety; measured using the SSS) are the endpoints collected daily through a diary. The BE diary will be filled in from the start of the screening period until EOT while the SSS will only be filled in during the first 2 weeks of treatment (from randomization [Visit 2] to Visit 4).

Table 6 defines the time windows used to calculate number of BE episodes/days per week.

Table 6Time windows (in days) to calculate weekly averages for the efficacy
endpoints BE episodes/days collected daily through the diary

Weeks	Study day (14-day window)
1–2	1–14
3–4	15–28
5–6	29–42
7–8	43–56
9–10	57–70
11–12	71–84

For the calculation of absence of BE episodes ('Yes'/'No') during the last 4 weeks of the treatment period, a minimum of 4 out of 7 diary entries are required for days 57–63, 64–70, 71–77 and 78–84, otherwise the outcome will be set to 'No absence'. Absence of BE episodes ('Yes') is defined as BE episodes equal to 0.

For the calculation of SSS, study days falling in the time window 2-15 will be considered for the analyses since study day 1 corresponds to assessments done on the day of the randomization where information on the SSS should not be collected.

11.8 Time window definitions for calculating exploratory efficacy and safety endpoints collected during site visits

The exploratory efficacy endpoints YBOCS-BE, PGI-S, CGI-S, PGI-C, CGI-C, EDE-Q, and HAMD-17 are collected during specific site visits [Table 7].

The safety endpoint C-SSRS[©] is collected during all site visits [Table 8].

For both efficacy and safety endpoints, if more than one assessment falls within the same time window, the assessment which is performed closest to the target study day will be considered for the analysis.

Table 7Time windows (in days) for visit-based exploratory efficacy
endpoints: YBOCS-BE, PGI-S, CGI-S, PGI-C, CGI-C, EDE-Q,
HAMD-17

Week	Target study day	Window	Endpoint
Baseline	1	1–1	YBOCS-BE, PGI-S, CGI-S, EDE-Q, HAMD-17
1	8	2-14	CGI-C, PGI-C
4	29	22-36	YBOCS-BE, PGI-S, CGI-S, PGI-C, CGI-C, EDE-Q
6	43	37–49	HAMD-17
8	57	50–64	YBOCS-BE, PGI-S, CGI-S, PGI-C, CGI-C, EDE-Q
12	85	78–92	YBOCS-BE, PGI-S, CGI-S, PGI-C, CGI-C, EDE-Q, HAMD-

CGI-C = Clinical Global Impression of Change scale; CGI-S = Clinical Global Impression of Severity scale; EDE-Q = Eating Disorder Examination Questionnaire; HAMD-17 = Hamilton Rating Scale for Depression (17-item); PGI-C = Patient Global Impression of Change scale; PGI-S = Patient Global Impression of Severity scale; YBOCS-BE = Yale-Brown Obsessive-Compulsive Scale modified for Binge Eating.

Table 8Time windows (in days) for C-SSRS©

Week	Target study day	Window	
Baseline	1	1–1	
1	8	5-11	
2	15	12–18	
4	29	22–36	
6	43	37–49	
8	57	50–64	
10	71	65–77	
12	85 78–92		

C-SSRS[©] = Columbia-Suicide Severity Rating Scale[©]

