- 8. All participants will be asked to return for an EOT visit. For participants who prematurely discontinue study treatment, the EOT visit will occur within 5 days of the last intake of study treatment. For participants who complete the treatment period as planned, the Week 12 visit corresponds to the EOT visit.
- 9. During unscheduled visits, additional assessments may be performed at the discretion of the investigator. The assessments in brackets are recommended to be performed on an unscheduled visit, based on medical judgment.

10. Stanford Sleepiness Scale to be filled in for the first 2 weeks of study treatment, twice daily, at breakfast (before morning dose) and around midday, prior to lunch time.

AE = adverse event; BP = blood pressure; BWSQ = Benzodiazepine Withdrawal Symptom Questionnaire; CGI-C = Clinical Global Impression of Change scale; CGI-S = Clinical Global Impression of Severity scale; C-SSRS© = Columbia Suicide Severity Rating Scale©; eCRF = electronic Case Report Form; ECG = electrocardiogram; EDE-Q: Eating Disorder Examination Questionnaire; EOS = End-of-Study; EOT = End-of-Treatment; HAMD-17 = Hamilton Rating Scale for Depression (17-item); ICF = informed consent form; IMP = Investigational Medicinal Product; IRT = Interactive Response Technology; MINI© = Mini International Neuropsychiatric Interview©; NA = not applicable; PGI-C = Patient Global Impression of Change scale ; PGI-S = Patient Global Impression of Severity scale; PK = pharmacokinetic(s); PR = pulse rate; RR = respiratory rate; SAE = serious adverse event; SCID-5 = Structured Clinical Interview for DSM-5; To = temperature; U1 = unscheduled visit; V = visit; WOCBP = women of childbearing potential; YBOCS-BE = Yale-Brown Obsessive-Compulsive Scale Modified for Binge Eating.

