#### 7.2.5.7 Columbia Suicide Severity Rating Scale©

The C-SSRS $^{\odot}$  is an instrument that reports the presence and severity of both suicidal ideation and behaviors.

Suicidal ideation is classified on a 5-item scale:

- 1. Wish to be dead
- 2. Non-specific active suicidal thoughts
- 3. Active suicidal ideation with any methods (no plan) without intent to act
- 4. Active suicidal ideation with some intent to act, without specific plan
- 5. Active suicidal ideation with specific plan and intent

The C-SSRS© also captures information about the intensity of ideation, specifically the frequency, duration, controllability, deterrents, and reasons for the most severe types of ideation.

In addition, the C-SSRS© captures information using yes/no questions and answers on suicidal behaviors, specifically: actual, interrupted, and aborted attempts; preparatory acts
or behaviors; and the presence of suicidal behaviors during the assessment period. More than one classification can be selected, provided they represent separate episodes. For actual attempts only, the actual or potential lethality is classified for the initial, most lethal, and most recent attempts.

At Screening the C-SSRS© will be completed for the study participant's lifetime history of suicidal ideation and behaviors and participants who answer "yes" *in the past month* to items 2, 3, 4, or 5 on the C-SSRS© assessment will be excluded from the study [see Section 5.4, criterion #26). At all other visits, the C-SSRS© will be completed for ideation and behaviors since the previous visit. All time points will be collected on a touchscreen device on site.

Participants who answer "yes" to items 2, 3, 4, or 5 on the C-SSRS© assessment at any post-randomization visit must undergo further evaluation by the investigator to assess the risk. No study treatment will be dispensed to such participants until after the investigator confirms suitability of the participant to remain in the study. This evaluation and decision should also be clearly recorded in the source documents.

As part of routine clinical care, participants will be provided with 24-hour emergency contact details in the event of an emergency should the participant feel that he/she is acutely at risk. In addition, participants who are recruited into the study will be advised of the location of their nearest hospital.

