# 9.2.10 Specific safety endpoints

*Daytime sleepiness* is defined daily as any score > 3 on the SSS after taking the morning dose. It will be collected on Days 1–14 and expressed as a number of days per week (as for the primary efficacy outcome). A minimum of 7 diary entries are required, otherwise the data will be considered missing. The mean number of days with daytime sleepiness per week will be summarized by treatment group.

The number (%) of study participants with *suicidal ideation and/or behavior* based on the C-SSRS© will be tabulated by visit and treatment group.

*Withdrawal effects* will be described summarizing changes from changes from Week 12/EOT to EOS in BWSQ and HAMD-17 by treatment group.

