2 STUDY DESIGN AND FLOW

[figure not shown]
This is a Phase 2, multicenter, double-blind, randomized, placebo-controlled, parallel-group, proof-of-concept study assessing ACT-539313 at a dosing regimen of 100 mg b.i.d. vs placebo over a 12-week treatment period in adult participants (18 to 55 years of age) with moderate to severe binge eating disorder (BED).

Approximately 120 participants will be randomized to either ACT-539313 at a dose of 100 mg b.i.d., or placebo in a 1:1 ratio.

The study will be conducted at approximately 30 sites in the USA.

The study design is shown in Figure 1.

Figure 1Study design for ID-082A201

b.i.d. = twice daily; EOS = End-of-Study; EOT = End-of-Treatment; V = Visit.

The study comprises the following 3 periods: the screening period, the treatment period and the safety follow-up period.

The **screening period** starts with the signing of the ICF at Visit 1 and ends with Randomization at Visit 2 or with a screening failure. It lasts a minimum of 14 days and up to 28 days.

The **treatment period** starts with the administration of the first dose of study treatment and ends on the day of the last dose of study treatment. The study participants will be treated for 12 weeks.

The **safety follow-up period** starts on the day after the last dose of study treatment and ends at the EOS visit (10 ± 3 days after EOT).

See Section 11.2 for detailed definitions of the study periods.

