7.8 Columbia-Suicide Severity Rating Scale[©]

The C-SSRS[©] is an instrument that evaluates suicidal ideation and behaviors.

The C-SSRS[©] outcome categories are provided below. Each category has a binary response (yes/no).

ACT-539313		Statistical Analysis Plan
ID-082A201	Confidential	for Clinical Study Report
1 April 2022, page 37/60	Confidential	Version 3
		Doc No D-22.100

- 1 Wish to be dead
- 2 Non-specific active suicidal thoughts
- 3 Active suicidal ideation with any methods (not plan) without intent to act
- 4 Active suicidal ideation with some intent to act, without specific plan
- 5 Active suicidal ideation with specific plan and intent
- 6 Preparatory acts or behavior
- 7 Aborted attempt
- 8 Interrupted attempt
- 9 Actual attempt (non-fatal)
- 10 Completed suicide

Categories 1-5 relate to suicidal ideation and a score of 0 is assigned if no suicidal ideation is present. Categories 6-10 relate to suicidal behavior.

Self-injurious behavior without suicidal intent is also a C-SSRS[©] outcome (although not suicide-related) and has a binary response (yes/no).

Based on the C-SSRS[©], the number (%) of study participants with suicidal ideation by category, suicidal behavior by category, suicidal ideation or suicidal behavior, and/or self-injurious behavior without suicidal intent, during the treatment period and the safety follow-up period will be tabulated. Percentages will be based on the number of study participants with at least one post-baseline C-SSRS[©] assessment. The assessments done at Week 1, 2, 4, 6, 8, 10, 12 will be assigned to the treatment period while the assessment done at EOS will be assigned to the safety follow-up period.

Shift from baseline showing any change in suicidal ideation and suicidal behavior during the treatment period and the safety follow-up period will be provided. Study participants will be summarized under the worst of the following three categories, shown here in the order from best to worst: 1) No suicidal ideation or behavior, 2) Suicidal ideation, and 3) Suicidal behavior (study participants with both suicidal ideation and suicidal behavior are also included in the suicidal behavior category).

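### Read literally, the closest-to-target rule in SAP 11.8 can leave a premature-EOT C-SSRS form out of the Section 7.8 suicidality tables, and SAP 7.8 and 11.2 can place that form in different periods (minor)

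*SAP*

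**What the plan says.** **Selection.** SAP 11.8 sets day windows for visit-based endpoints. For efficacy and safety alike, "if more than one assessment falls within the same time window, the assessment which is performed closest to the target study day" is the one used. Table 8 gives the C-SSRS windows: Baseline and Weeks 1, 2, 4, 6, 8, 10 and 12. It has no row for a premature EOT visit or for EOS.

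**Analysis.** SAP 7.8 plans the only C-SSRS tables: incidence by category in the treatment and follow-up periods, and a shift table by worst category. Percentages use participants with at least one post-baseline form. The Week 1 to 12 assessments "will be assigned to the treatment period while the assessment done at EOS will be assigned to the safety follow-up period".

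**Collection.** Protocol Table 1 schedules a C-SSRS at every visit, including EOT. Its footnote 8 says: "For participants who prematurely discontinue study treatment, the EOT visit will occur within 5 days of the last intake of study treatment". Under Protocol 7.2.5.7, post-screening forms "will be completed for ideation and behaviors since the previous visit".

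**Periods.** SAP 11.2 runs the treatment period to EOT (Week 12) or, "for those who prematurely discontinued study treatment (i.e., those without an EOT date), until the day of study treatment end date". Follow-up then runs from the day after EOT to EOS.

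**The concern.** Table 8 exists only for the C-SSRS, and the 7.8 tables are the only C-SSRS analyses. A programmer who follows 11.8 to the letter would therefore pass the forms through Table 8 before building those tables. A premature EOT visit comes 1 to 5 days after the last dose, so it can share a window with the scheduled visit just before it. If that visit was nearer its target day, the EOT form is not used. Because each form looks back only to the previous visit, no later form covers the interval.

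The form at risk is the one completed as a participant leaves treatment, and suicidality is a named safety endpoint. Early stopping did occur: SAP 14.4 refers to 9 participants who discontinued because of site closure. The second question is the period. Because 7.8 tabulates by period, two programmers could report the same form in different columns.

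**Working it through.** The plan gives no figure here to reproduce. The check applies the stated rules to dates.

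**Inputs.** Table 8 (target; window): Week 1 (8; 5-11), Week 2 (15; 12-18), Week 4 (29; 22-36), Week 6 (43; 37-49), Week 8 (57; 50-64), Week 10 (71; 65-77), Week 12 (85; 78-92). Protocol Table 1: premature EOT 1-5 days after last dose; EOS 10 ± 3 days after EOT.

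**Route 1, shared window.** Week 4 visit Day 29, last dose Day 30, EOT Day 32. Both visits fall in 22-36. Distances from target are |29 − 29| = 0 and |32 − 29| = 3, so the Day 29 form is used. Any Week 4 visit on Days 27-31 gives the same result against an EOT on Days 32-36: the distance is at most 2 against at least 3.

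**Route 2, no window.** Days 2-4 and 19-21 are uncovered. Scheduled visits held within their protocol windows never fall there, but a premature EOT can.

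**Illustration.** Assume the last dose is equally likely on Days 1-83 and the EOT delay is equally likely to be 1-5 days: 83 × 5 = 415 combinations. A form counts as unused if its day is in no window, or if a scheduled visit on or before the last dose was strictly closer to target.

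| Scheduled visits held | Superseded + no window | Share of 415 |
|---|---|---|
| At late limit | 54 + 21 = 75 | 18% |
| 1 day late | 76 + 21 = 97 | 23% |
| On target | 102 + 21 = 123 | 30% |
| At early limit | 102 + 21 = 123 | 30% |
| 1 day early | 112 + 21 = 133 | 32% |

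The early-limit and 1-day-early rows leave 22 and 12 ties uncounted; 11.8 has no tie rule. The counts also leave out the participant's own EOS form. If that too were windowed by day, then with visits on target a further 15 (EOS 12-13 days after EOT) to 90 (7 days after) combinations would lose the EOT form.

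**Is Table 8 meant as a filter?** For completers, EOT on Days 83-87 and EOS 7-13 days later give 5 × 7 = 35 combinations. In 29 the EOS day is past Day 92 and has no window. In the other 6 it lies in 78-92 but farther from Day 85 than the Week 12 visit. A strict filter would thus discard all 35 EOS forms, although 7.8 assigns EOS to follow-up.

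**Period of the Day 32 form.**

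| Rule | Result |
|---|---|
| SAP 7.8, by visit | Not EOS; Week 4 in Table 8, or nominally the Week 12 / EOT visit: treatment |
| SAP 11.2, by date, EOT = last dose (Day 30) | Treatment ends Day 30, follow-up starts Day 31: follow-up |
| SAP 11.2, by date, EOT = visit (Day 32) | Treatment ends Day 30, follow-up starts Day 33: neither |

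The parenthesis in 11.2 adds doubt. A participant who attends the premature EOT visit does have an EOT date, and someone applying the Week 12 branch on that ground would reach the treatment period.

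**The case against.** The best defence is that 7.8, the specific section, already implies that all forms count. It classifies by worst category, its denominator needs only one post-baseline form, and it uses EOS forms for which Table 8 has no row. A closest-to-target rule serves a by-visit display, and 7.8 plans none. This is good evidence of intent. It does not settle the matter, because the worst-category wording does not say which forms enter, and 11.8 names safety endpoints without limiting itself to by-visit displays.

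Three stronger readings are tempting but not supported.

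- *A general conflict among SAP Section 2, 7.8, 11.2 and Table 8.* Section 2 says follow-up "starts on the day after the last dose of study treatment and ends at the EOS visit", but it refers to 11.2 for the detailed definitions, so it is not a competing rule. Protocol 7.1 equates EOT with the last dose; on that meaning 11.2 agrees with Section 2. Table 8 week labels lead to the treatment period, as in 7.8. One mismatch remains, between 7.8 and 11.2.
- *That 18% to 32% of premature-EOT forms would be lost.* Those are shares of calendar combinations under an assumed uniform last-dose day, not of participants or events, and they omit the EOS form.
- *That suicidality would go unseen.* SAP 7.1 lists all safety data, and Protocol 7.2.5.7 requires investigator evaluation after any post-randomization positive answer to items 2-5.

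Unscheduled forms are a side issue. Protocol Table 1, footnote 9, says "During unscheduled visits, additional assessments may be performed at the discretion of the investigator", but Table 1 schedules no C-SSRS there, so no figure is offered.

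**Conclusion.** The point holds as a minor one. Applied as written, SAP 11.8 can exclude a premature-EOT C-SSRS from the only suicidality tables, contrary to the apparent purpose of 7.8. Visit-based 7.8 and date-based 11.2 can also assign that form to different periods, and the 11.2 phrase about having no EOT date does not fit the protocol's premature EOT visit.

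The exclusion depends on a literal reading of 11.8; if every form is used, none is lost. The documents give neither discontinuation times nor a suicidality rate, so neither the frequency nor any bias in incidence can be computed. The effect is limited to descriptive summary tables.

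**What to change.** - In SAP 7.8, state that the incidence and shift tables use every C-SSRS form after first dose (scheduled, premature EOT, any unscheduled, EOS), taking the worst category per period.
- In SAP 11.8, confine Table 8 and the closest-to-target rule to by-visit displays.
- Reconcile 7.8 and 11.2 into one period rule for premature-EOT forms, say whether EOT in 11.2 means the last dose or the visit, and correct the parenthesis.
- As housekeeping, Protocol 9.2.10 says suicidality "will be tabulated by visit and treatment group". SAP 7.8 has no by-visit table and SAP 12.1 does not list its removal. Either plan it or record the change.

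The cost is one SAP paragraph, a wording correction in 11.2 and a small programming change. No extra data are needed.
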